### ABSTRACT

Rationale: Men who have sex with men (MSM) continue to be disproportionately affected by HIV. The majority of HIV infections among MSM occur through exposure to the rectal mucosa during receptive anal intercourse (RAI). To aid in prevention, a new HIV prevention intervention, called pre-exposure prophylaxis (PrEP), recommends that MSM at risk of HIV infection take a daily anti-HIV medication called Truvada® (tenofovir/emtricitabine) which is shown to be highly effective. However, current tenofovir- based regimens have shown to cause different side effects while taken. To reduce these side effects, new formulations of anti-HIV agents are being developed, but the ability of these new agents to penetrate mucosal tissues and prevent HIV infection at sites of virus exposure is unclear.

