**Design:** To address the efficacy of the new formulated anti-HIV agents and their ability to penetrate the mucosal tissues in MSM, investigators at Emory University will collaborate with the Centers for Disease Control and Prevention (CDC) to conduct a randomized clinical trial of 90 MSM. Men will be randomized into a 2-arm study (fortyfive men assigned to each arm) as follows: (Arm 1) daily oral Truvanda® or (Arm 2) daily oral Genvova®. Each study arm includes 3 phases: (1) pre-drug, (2) short-course, and (3) steady state. For phase I, there will be 5 men assigned to both arm 1 and arm 2. Phases II and III will each have 20 men assigned to both arms. The study will entail 2 study visits for phase I, 3 study visits for phase II, and 4 study visits for phase III at the Emory University Hope Clinic. During phase I: visit 1, all men will be screened for eligibility and undergo written informed consent, physical examination, rapid HIV testing, phlebotomy for screening laboratories, and randomization. During study visit 2 (time 1-6 weeks after study visit 1), participant returns and a urethral swab, 2 pre- wet penile swabs, and a urine sample will be collected. Participant will then undergo a rectal biopsy via rigid sigmoidoscopy for establishment of baseline values. During phase II: study visit 1, men will be screened for eligibility and undergo written informed consent, physical examination, rapid HIV testing, phlebotomy (will collect 4 tablespoons) for screening laboratories, and randomization. During study visit 2 (time 1-6 weeks after study visit 1), men will be dispensed and instructed to take either one dose of Truvada® or Genvoya®. After 4 to 6 hours after dosing, a urethral swab, 2 pre- wet penile swabs, 4 tablespoons of blood, and a urine sample will be collected. During study visit 3 (time 24 hours after drug dosing), men will return after 24 hours of study product use for repeat phlebotomy, urethral and penile swabs, collection of urine and rectal secretions, and rectal biopsy via rigid sigmoidoscopy. For phase III: visit 1,

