men will be screened for eligibility and will undergo the informed consent process. Once informed consent is signed, a physical examination will be performed, rapid HIV testing, phlebotomy for screening labs, and randomization will occur. During study visit 2 (time 1-6 weeks after study visit 1), men will be dispensed and instructed to take either Truvada® or Genvoya® for 10 days. After 3 to 5 consecutive days of dosing, participants will return for visit 3 where a urethral and penile swabs specimen, blood work, and a urine specimens will be obtained. During study visit 4 (time 10 days of consecutive drug dosing), men will return for repeat phlebotomy, urethral and penile swabs, collection of urine and rectal secretions, and rectal biopsy. After collection, biologic specimens will be immediately transported by courier to CDC (laboratory of [name]) for processing. Specimens will be processed immediately for ex vivo laboratory assays that will include Truvada® and/or Genvoya® drug concentrations, inflammatory cytokine levels, HIV target cell measurement and characterization by flow cytometry, and in vitro HIV infection assays. Comparison of assay results between the 2 study arms will help in determining the ability of the new formulated anti-HIV drug to penetrate different body compartments at the site of possible HIV exposure.

Participants may participate in more than one phase; however, at least 8 weeks must lapse after completion of 1 study phase before entry into another. Men who participate in more than one phase will not be consented again and do not have to repeat the screening visit (visit 1) when starting another phase; they will begin the new phase at visit 2.

Duration: The duration of this study is 3 years. Participants will be considered 'on-study' for no more than 12 weeks.

Sample size: For this protocol we will recruit 90 HIV-negative MSM or transgender women who are not taking hormone therapy who meet eligibility criteria outlined in the protocol.

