For this protocol, we will recruit HIV-negative MSM and TGW who are not on hormone therapy aged 18-49 and who are willing to adhere to study procedures. There will be 3 phases, with 2 study visits for phase I, 3 study visits for phase II, and 4 study visits for phase III that will be conducted over a maximum period of 12 weeks. Participants are allowed to participate in more than one phase if a recovery or washout period occurs 8 weeks in between each phase. The first visit for all phases (phase I, phase II, and phase III) will be a screening visit where eligibility is determined, written informed consent is obtained, screening tests are performed, and men will be randomized to one of two study groups: 1. Use of oral Truvada®; or 2. Use of oral Genvoya®. During the second study visit (visit 2), men in phase I will not receive product, but will come in for blood work, urine sample, 2 pre-wet penile swabs, urethral swab, rectal swab, and rectal biopsy sampling. Participants who are in phase II will receive a single dose of the study product during visit 2, 1-6 weeks after the screening visit. MSM will return 4 to 6 hours after taking the drug for a urine sample. We will then collect 4 tablespoons of blood from the participants arm, in addition to, 2 pre-wet penile swabs, and a urethral swab. The third study visit will occur 24 hours from dosing time for MSM in phase II. Men will undergo a blood draw, urine sample, penile, urethral, and rectal swab, and rigid sigmoidoscopy for collection of rectal secretions and biopsies. Participants in phase III at study visit 2 will receive a 10-day supply of the study drug and will be instructed to take it for 10 consecutive days. For visit 3 in phase III, participants will return for a blood draw, urine collection, 2 pre-wet penile swabs, and a urethral swab to examine drug levels after 3-5 days of taking study drug. They will then return 10 days from dosage for visit 4, where blood, urine, penile, urethral, and rectal swabs will be collected, and rectal biopsy sampling will occur. All specimens will be transported directly to the laboratory of [name] at CDC where multiple immune assays are planned to determine the ability of these agents to penetrate mucosal tissues and potentially prevent HIV infection during RAI exposure.

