# PROJECT DESCRIPTION

**Public Health Relevance:** Information about new anti-HIV agents and how they penetrate through mucosal tissues will better inform scientists about the potential of new agents to be used for pre-exposure prophylaxis (PrEP).

**Goal**: To compare the body compartment pharmacokinetics and mucosal inflammatory effects of Truvada® vs. Genvoya®.

Version 6 04/21/17

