Unique Protocol ID: IRB00092488

NCT02985996

Statistical Analysis Plan

Truvada® vs. Genvoya®

Principal Investigator [name] [name]

01/15/2019

Demographic, behavioral, clinical, and laboratory data will be collected from the screening clinical assessment, the study entry physical examination and screening laboratory tests, and rectal biopsy visits.

Median (range) drug levels will be calculated at baseline and each of the protocol specified follow-up time points. Differences in median drug levels between baseline and study visit follow-up visits will be analyzed with non-parametric Wilcoxon-signed rank tests. A p-value of <0.05 will be considered significant.

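### The SAP contains no Truvada versus Genvoya analysis: its only test compares an undefined baseline with follow-up within person, and rectal tissue has no within-phase pairs for it

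*SAP*

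**What the plan says.** The goal in the protocol's Project Description is "To compare the body compartment pharmacokinetics and mucosal inflammatory effects of" Truvada and Genvoya. The Abstract says how the question is to be answered: "Comparison of assay results between the 2 study arms will help in determining the ability of the new formulated anti-HIV drug to penetrate" (the sampled compartments). It also lists the laboratory outcomes other than drug concentration: "inflammatory cytokine levels, HIV target cell measurement and characterization by flow cytometry, and in vitro HIV infection assays". The motivation is that "the ability of these new agents to penetrate mucosal tissues and prevent HIV infection at sites of virus exposure is unclear".

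The SAP has two analysis elements. One is the median and range of drug levels at baseline and at each follow-up time. The other is "Differences in median drug levels between baseline and study visit follow-up visits will be analyzed with non-parametric Wilcoxon-signed rank tests", with significance at p below 0.05. Apart from the title, it mentions neither product and no study arm.

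Baseline is not defined in the SAP. For study specimens, the protocol uses the word only in its account of Phase I: "Participant will then undergo a rectal biopsy via rigid sigmoidoscopy for establishment of baseline values". The Lay Summary adds that "men in phase I will not receive product". Men may enter more than one phase after an 8-week gap, skipping the screening visit, and "they will begin the new phase at visit 2".

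**The concern.** The randomised contrast is the reason for having two arms, and neither document specifies how it will be analysed. The protocol announces an arm comparison without a method, and the SAP supplies a method for a different question.

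On a pre-drug reading of baseline, a significant signed-rank result shows only that dosing raises drug levels in men who were required not to be on PrEP. On a first-on-drug-sample reading, it shows only that levels change with time. Neither says how the two products differ. The inflammatory half of the goal has no analysis at all.

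The test, analyte, compartment, time point, phase and handling of values below quantification for the arm comparison are therefore open to choice after the data are seen, with 0.05 available for each combination.

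**Working it through.** **The plan's own figures.** Phase sizes per arm are 5, 20 and 20 (Study visits, Visit 2), so 2 × (5 + 20 + 20) = 90. With 20% not completing (Study Population), 90 × 0.8 = 72. Both agree with the protocol. Per arm, completers are 20 × 0.8 = 16 in each of Phases II and III and 5 × 0.8 = 4 in Phase I. No power, effect size or SD is given, so there is no power statement to reproduce.

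**What is sampled, and when** (Study visits, Visits 1 to 4):

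| Phase | Drug given | Blood, urine, penile and urethral samples | Rectal samples |
|---|---|---|---|
| I | none | visit 2 | visit 2 |
| II | single dose | visit 2 (4–6 h after dose), visit 3 (24 h) | visit 3 only |
| III | 10 days | visit 3 (day 3–5), visit 4 (day 10) | visit 4 only |

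Screening blood at visit 1 is listed for blood count, creatinine and coagulation. The text describes no pre-dose study specimen in Phases II or III.

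**Reading (a): baseline means pre-drug.** Phases II and III hold 40 + 40 = 80 of 90 places and have no within-phase pre-drug/on-drug pairs in any compartment. Pairs can come only from Phase I men who also join another phase, so at most 10 men. If they keep their arm, that is at most 5 per arm, or 4 after loss.

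The smallest exact two-sided signed-rank p is 2/2ⁿ:
- n = 4: 0.125
- n = 5: 0.0625
- n = 6: 0.031
- n = 10 (arms pooled): 0.002

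So an exact two-sided test within an arm could not reach 0.05. This floor is conditional. For 5 same-sign pairs, W = 15, its mean is 7.5 and its variance is 5 × 6 × 11/24 = 13.75. Then z = 7.5/3.708 = 2.02 (p = 0.043), or 7.0/3.708 = 1.89 (p = 0.059) with continuity correction. The one-sided exact p is 0.031.

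If an analyst instead set every pre-drug level to zero, all differences would be positive and the p-value would depend on n alone. With 16 per arm it is 2/2¹⁶ = 0.00003 in both arms, whatever the ratio between them.

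**Reading (b): baseline means the first on-drug sample.** Phase II visit 2 against 3, and Phase III visit 3 against 4, give up to 20 pairs per arm per phase (16 after loss) for four sample types. They give none within a phase for rectal samples.

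**No arm contrast.** The signed-rank statistic uses the signs and ranks of within-person differences. Multiplying all levels in an arm by c > 0 multiplies every difference by c and changes neither. This is algebra and needs no assumed SD.

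A simulation shows the consequence. It used 4,000 runs, 16 per arm, assumed between-person log SD 0.83, a within-person log change of −0.5 (SD 0.5), and exact two-sided tests at 0.05. The signed-rank test was run on raw level differences.

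| True arm ratio | Signed-rank rejects, arm 1 / arm 2 | Between-arm rank-sum at follow-up rejects |
|---|---|---|
| 1 | 83.1% / 82.8% | 5.1% |
| 2 | 84.0% / 84.1% | 47.5% |
| 4 | 83.8% / 82.8% | 96.9% |

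On log differences the signed-rank rate is about 95%, again the same at every ratio.

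**Precision of a between-arm analysis.** With 16 per arm, the 95% CI for a geometric mean ratio is the estimate divided by and multiplied by exp(t₀.₉₇₅,₃₀ × SD × √(2/16)). With t = 2.042, the factor is 1.40, 1.82 and 2.56 for assumed log SDs of 0.47, 0.83 and 1.3. The simulated follow-up values have log SD √(0.83² + 0.5²) = 0.97, which gives 2.01, within that range.

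**The case against.** The strongest reply is that this is a small exploratory pharmacokinetic study. No hypothesis, primary endpoint or power is stated, and the visit text describes the blood, urine and swab samples as serving assay development. The protocol already says the arms will be compared, so a formal primary contrast could be called a preference. That supports estimation over testing. It does not support omitting the randomised contrast, and nothing in either document supplies it.

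Some narrower points stand:
- The p-value floor for 5 pairs depends on the choice of test, on sidedness and on men keeping their arm. The documents are unclear on the last. The Abstract and Lay Summary put randomisation at visit 1, which returning men skip, and the Phase II and III visit text speaks of reviewing an existing assignment. The Visit 2 section, however, lists randomisation there. Keeping the arm is the likelier reading.
- Men who join both Phases II and III could give cross-phase on-drug rectal pairs. The absence of rectal pairs is a within-phase statement.
- Figure 1 is not available, so a pre-dose sample shown only there cannot be excluded. The Abstract gives the Phase II screening draw as 4 tablespoons, the volume used for study draws, but labels it for screening laboratories.
- The simulation rests on assumed SDs and on the scale chosen.

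None of these creates an arm comparison or an inflammatory-marker analysis.

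**Conclusion.** The concern holds, with high confidence, and must be fixed. Followed exactly, the SAP yields no Truvada versus Genvoya result for any outcome, and its one test cannot substitute for that result under either reading of baseline. The missing arm contrast, the missing inflammatory analysis and the undefined baseline follow directly from the text.

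The pair counts rest on the visit text without Figure 1: no within-phase pre-drug pairs for 80 of 90 places, and no within-phase rectal pairs in any phase. The p-value floor, simulation rates and interval widths are illustrations under the stated assumptions. The conclusion does not depend on them.

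**What to change.** Make the between-arm comparison the main analysis:

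- **Method.** Within each of Phases II and III, by compartment and time point, compare the arms as randomised with a Wilcoxon rank-sum test. Report a Hodges-Lehmann or geometric mean ratio with a 95% CI.
- **Inflammatory markers.** Apply the same comparison, and state how the target-cell and in vitro infection assays will be analysed.
- **Values below quantification.** State a rule. One example is to rank them tied lowest, report the number per arm, substitute half the limit for the ratio with a sensitivity analysis, and give only proportions if more than half of either arm is below.
- **Primary contrast.** Preferably name one, tested at 0.05, for example rectal tissue at Phase III visit 4. The sponsor should justify an analyte measurable in both arms that addresses tissue penetration of the new agent. Emtricitabine is in both products but may not do so alone. Label the rest secondary or exploratory.
- **Baseline.** Define it. Treat Phase I as descriptive pre-drug reference values, and keep the signed-rank test as a secondary comparison of on-drug times (Phase II visit 2 against 3, Phase III visit 3 against 4).
- **Returning men.** State whether they keep their arm, and reconcile the visit at which randomisation occurs.
- **Status.** Date the change and label it post hoc if data have already been seen.

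The first two items and the definition of baseline cure the defect. The single primary contrast and the particular quantification rule are recommendations that can be varied.

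The cost is SAP wording and modest extra analysis, with no new participants, visits or samples. Fewer p-values could be called confirmatory, and with about 16 per arm per phase the intervals may be wide: a factor of 1.4 to 2.6 either way under the assumed SDs.

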# Visit 1

# Phase I, II, and III

During the screening visit, eligible MSM will provide written informed consent after all their questions are answered in a private exam room at the Hope Clinic. Subjects will also receive an approved HIPAA statement and will be informed about the way their protected health information will be used and stored. Copies of the consent/HIPAA form for this project will not be placed in individuals' medical records since this study collects sensitive information such as HIV status and sexual orientation.

After provision of informed consent, a medical history and physical examination will be conducted by the PI to evaluate for exclusion criteria. A rapid HIV test with finger stick whole blood (Determine or other CLIA waved product) will be performed by the PI or study coordinator who will be certified in HIV counseling and testing to confirm eligibility. Peripheral blood will be drawn for a complete blood count, creatinine, and coagulation tests.

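### The SAP's only test sets drug levels at an undefined baseline against follow-up, so it does not compare the two drugs

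*SAP*

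**What the plan says.** The SAP's analysis is two sentences and a significance threshold of 0.05. The first is descriptive: "Median (range) drug levels will be calculated at baseline and each of the protocol specified follow-up time points". The second gives the only test: "Differences in median drug levels between baseline and study visit follow-up visits will be analyzed with non-parametric Wilcoxon-signed rank tests". Neither mentions study arm, and baseline is not defined.

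The Protocol's goal (PROJECT DESCRIPTION) is comparative: "To compare the body compartment pharmacokinetics and mucosal inflammatory effects of" the two products. The ABSTRACT says the same of the laboratory results: "Comparison of assay results between the 2 study arms will help in determining the ability of the new formulated anti-HIV drug".

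The Protocol uses the word baseline in two ways. For Phase I visit 2 the ABSTRACT says "Participant will then undergo a rectal biopsy via rigid sigmoidoscopy for establishment of baseline values". Exclusion criterion 2 uses it for a visit at which eligibility laboratory values are judged. On the first use, the LAY SUMMARY states that "men in phase I will not receive product". On the second, the Visit 1 section says "Peripheral blood will be drawn for a complete blood count, creatinine, and coagulation tests", and lists no drug assay.

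**The concern.** The trial randomises participants to two drugs in order to compare them, yet the one planned test never sets one arm against the other. Followed exactly, the SAP could report significant results in both arms whether the drugs reach tissue equally well or very differently.

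The undefined baseline adds a second problem. On the meaning with most support in the Protocol, few pairs or none may exist. On the alternatives an analyst might turn to, the test answers a minor question. Leaving the choice open also lets it be made after results are seen. Rectal tissue, the exposure site on which the rationale rests, is worst placed: no measured baseline assures it a within-participant pair.

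**Working it through.** **Inputs.** Phase I: 10 participants, 5 per arm. Phases II and III: 40 each, 20 per arm (ABSTRACT; Visit 2 sections). The Phase III paragraph prints the wrong phase number, but the ABSTRACT confirms the count. Non-completion: 20% (STUDY POPULATION). Threshold: 0.05 (SAP), taken as two-sided because the SAP does not say. Neither document gives an SD, an effect size or a power statement.

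**The plan's own figures.** Places: 2×5 + 2×20 + 2×20 = 90. Completers: 90 × 0.80 = 72. Both reproduce. The same loss applied to one arm of Phase II or III gives 20 × 0.80 = 16.

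**What baseline could mean.** The smallest exact two-sided signed-rank p with k non-zero differences, all of one sign, is 2/2^k.

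1. *Phase I pre-drug visit* (best supported). These participants are undosed, and entering another phase is optional. Measured pre-dose pairs assured by the visit text: 0 of 40 + 40 = 80 dosed places. If all 5 in an arm re-entered and kept that arm, the smallest p is 2/2^5 = 0.0625, so 0.05 is out of reach. Pooling all 10 gives 2/2^10 = 0.002, but mixes the two drugs.
2. *Screening visit.* No drug assay is listed, and blood is the only specimen described there.
3. *First on-drug sample* (an analyst's choice, with no support in the text). Pairs exist for blood, urine, penile and urethral specimens: 4–6 hours against 24 hours in Phase II, and visit 3 against visit 4 in Phase III. Both members of each pair are post-dose. Rectal secretions and biopsies are taken once per phase, so they have no pair.
4. *Fixed zero* (also an analyst's choice). The test runs for every specimen but shows only that drug was detectable: 2/2^16 = 3.05e-5 with 16 quantifiable participants, and 2/2^20 = 1.9e-6 with 20.

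**Does any of these compare the drugs?** No. Under 3 and 4, multiplying every level in one arm by ten changes no sign and no rank, so that arm's p-value does not move. A simulation under 4 shows the effect (20 per arm, 2000 runs, lognormal levels, log SD of 1 assumed):

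| True ratio between arms | Both within-arm signed-rank tests significant | Between-arm rank-sum test significant |
|---|---|---|
| 1 | 100% | 4% |
| 3 | 100% | 92% |

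**What a between-arm test could detect.** Two-sided t-test at 0.05, 80% power, with n multiplied by 0.955 for the rank-sum test: 1.05 SD of log level with 16 per arm, 0.93 SD with 20. The SD has to be assumed. Over a range of 0.5 to 1.5 on the natural-log scale, the detectable ratio runs from exp(0.93 × 0.5) = 1.6 to exp(1.05 × 1.5) = 4.8.

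**The case against.** The strongest reply is that the intent to compare arms is plain from the Protocol's goal, its ABSTRACT and the SAP's own title, and that the medians could simply be tabulated by arm. The intent is indeed clear, so a reader should not infer that the trial never meant to compare the drugs. But none of those places names a method or an estimate, and the one method that is named cannot do the job.

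A second reply is that baseline is less open than it looks, because the ABSTRACT links baseline values to Phase I. That stands: the four meanings above are not equally supported, and the last two are only what an analyst might fall back on. The Phase I meaning, however, is the one under which pairs are not assured.

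A reader might also infer that the test cannot be run, or that no pre-dose sample exists. The documents do not support either. The test runs on the first on-drug sample or against zero. Phase I participants may re-enter. The Phase II screening visit is described as "phlebotomy (will collect 4 tablespoons) for screening laboratories, and randomization", and 4 tablespoons is also the volume drawn at the research visits, so that blood could be assayed, though no drug assay is stated. Figure 1 is not shown and could not be checked for a pre-dose sample. Even a pre-dose sample for everyone would leave the arms uncompared.

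**Conclusion.** The concern holds and should be fixed before analysis. The SAP's only test compares times within participants and on no meaning of baseline compares the two randomised arms, which is the stated goal. That conclusion rests on the text alone.

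The pairing problem is second and is limited to what the visit text assures: 0 of 80 dosed places with a measured pre-dose pair. The 0.0625 floor assumes a two-sided test and that re-entering participants keep their arm. The Protocol leaves the latter unclear, since it places randomisation at visit 1 in the ABSTRACT and at visit 2 under Study visits. The very small p-values apply only if zero is taken as baseline.

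**What to change.** 1. **Main analysis.** Compare the arms at each phase and time point with an unpaired two-sided rank-sum test, rectal specimens included, ranking unquantifiable values as tied lowest. Report medians by arm and a between-arm estimate with a confidence interval, for example the Hodges-Lehmann shift on log levels read as a ratio, where enough values are quantifiable. Name one main contrast (for example, rectal biopsy at Phase III visit 4) and one analyte measured in both arms, chosen by the sponsor before analysis. If a tenofovir form is used, name the form assayed. The specimens allow 4 types × 4 time points + 2 rectal types × 2 time points = 20 between-arm comparisons per analyte. Label all but the main one exploratory, for every analyte.
2. **Signed-rank tests.** Keep them, by arm and labelled exploratory, only where pairs exist: first post-dose sample against 24 hours in Phase II, and visit 3 against visit 4 in Phase III, in blood, urine, penile and urethral specimens. That is 4 × 2 phases × 2 arms = 16 per analyte.
3. **Baseline.** Define it as Phase I visit 2 with both arms pooled. Report it descriptively as drug-free reference values, and do not use it as a paired baseline.

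**Cost.** The change is to SAP wording, plus reconciling the Protocol's two descriptions of the first Phase II sampling time: 4–6 hours under Visit 2, and 6 hours ± 2 (that is, 4–8 hours) under INCENTIVES. No new specimens are needed. The downside is some extra analysis and modest precision, with only differences of about 0.93 to 1.05 SD detectable at 80% power. The mucosal inflammatory half of the goal still needs its own analysis; this fix does not supply one.

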# Phase I

10 participants (5 in each study arm) will be enrolled in study phase 1.

Study visit 2 will occur 1-6 weeks after the screening visit. During visit 2, we will draw 4 tablespoons of blood from the participants arm. A urine sample as well as penile and urethral swabs will be collected from participants. These samples will be used at CDC to develop an assay to detect Truvada® and Genvoya® in the body compartments. All specimens will be coded with a unique numeric identifier such that the CDC laboratories that receive the specimens will be unable to link them back to the study participants. Finally, rigid sigmoidoscopy (described further below) will be performed and, rectal secretions will be collected with Dacron swabs, and 8-12 rectal biopsies will be collected. A rectal swab will be collected for testing for gonorrhea and chlamydia to be performed by CDC. If positive for gonorrhea or chlamydia, men will be referred for care at their private physician's office, the health department, or AID Atlanta for treatment. All men will be instructed to place nothing in the rectum and to abstain from sex for 7 days after the procedure to allow the mucosa to heal.

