# Phase II

40 participants (20 in each study arm) will be enrolled in study phase 2.

Study visit 2 will occur 1-6 weeks after the screening visit. During visit 2, the study group assignment will be reviewed and participants will be provided with a single dose of Truvada® or Genvoya®. Drug will be dispensed through the Emory Investigational Drug Service. Depending on the study arm they were assigned to, MSM will be dispensed 1 day of Truvada® or Genvoya® and instructed on dosing for that day. Four to six hours after the drug is taken, a urine sample, 4 tablespoons of blood will be drawn from the participants arm, as well as, penile and urethral swabs will be collected from participants. These sample will be used at CDC to develop an assay to detect Truvada® and Genvoya® in the body. All specimens will be coded with a unique numeric identifier such that the CDC laboratories that receive the specimens will be unable to link them back to the study participants. Participants will be requested to abstain from receptive anal intercourse 3 days prior to study visit 2 and while taking study product.

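### The SAP's only test, a signed-rank comparison with baseline, does not show whether drug typically reaches a compartment, whether baseline is assumed or measured

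*SAP*

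**What the plan says.** The SAP's analysis text is three sentences. It first describes: "Median (range) drug levels will be calculated at baseline and each of the protocol specified follow-up time points". It then tests: "Differences in median drug levels between baseline and study visit follow-up visits will be analyzed with non-parametric Wilcoxon-signed rank tests". It closes with the criterion: "A p-value of <0.05 will be considered significant". It does not state:

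- sidedness, or exact versus approximate p-values;
- the treatment of zero differences;
- a quantification limit, or how values below it are coded;
- what baseline means for a man in Phase II or III;
- whether arms are pooled;
- any confidence interval.

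In the Protocol, the term baseline is attached to Phase I, where no drug is given: "Participant will then undergo a rectal biopsy via rigid sigmoidoscopy for establishment of baseline values" (Abstract). Under Study visits, Phase I is small: "10 participants (5 in each study arm) will be enrolled in study phase 1". Phase II is larger: "40 participants (20 in each study arm) will be enrolled in study phase 2". The Phase III section gives the same numbers, and the Abstract confirms 20 per arm. In Phase II the first drug-level sample is taken after dosing: "Four to six hours after the drug is taken, a urine sample, 4 tablespoons of blood will be drawn". In Phase III the first is at Visit 3, after 3 to 5 days on product. Blood at Visit 1 is for safety laboratories only.

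On purpose, the Abstract says that the comparison of assay results between the two arms "will help in determining the ability of the new formulated anti-HIV drug to penetrate different body compartments".

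**The concern.** A signed-rank test asks whether paired differences are symmetric about zero. The SAP reads its p-value as a statement about medians. The two can part company when many values are below quantification.

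Inclusion criterion 4 requires that men are not taking PrEP, so a pre-drug level can reasonably be assumed below the limit. Against such a baseline a difference cannot be negative. It is zero in a man without measurable drug and positive in a man with it. The p-value then depends essentially on how many men had any measurable drug. It says little about the men in whom none was found.

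The trial is about penetration of urine, penile and urethral surfaces, rectal secretions and rectal tissue, in Phase II after a single dose. The p-value is the only inferential result planned. A compartment in which most men had no measurable drug could be reported as a significant change in median level, with no estimate of size or precision to correct that impression.

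**Working it through.** **Inputs.** Test and alpha come from the SAP. Sizes are 20 per arm or 40 pooled in each of Phases II and III, and 5 per arm in Phase I (Protocol, Study visits). Non-completion of about 20% is from Study Population: 20 × 0.80 = 16 and 40 × 0.80 = 32. Two inputs are assumed: the pre-drug level is below quantification, and testing is two-sided. Detection rates are not in the documents, so a range is shown.

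**Plan's own figures.** There is no power or precision calculation to reproduce. The head counts agree: 2 × (5 + 20 + 20) = 90 and 90 × 0.80 = 72.

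**Reading A: baseline taken as below quantification for every man.**

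1. Let k be the number of men with measurable drug at follow-up. With zeros dropped, k differences remain, all positive. Of the 2^k equally likely sign patterns one is all positive, so two-sided exact p = 2 × (1/2)^k.
2. k=5 gives 2/32 = 0.0625. k=6 gives 2/64 = 0.031. The number of men sampled does not enter, so this is the same for 16, 20, 32 or 40.
3. The follow-up median stays below quantification for up to 7 of 16, 9 of 20, 15 of 32 or 19 of 40 men detected. So 6 of 20 (30%; exact 95% CI 12% to 54%) or 6 of 40 (15%; 6% to 30%) is significant with both medians below the limit.
4. The threshold depends on choices the SAP leaves open:

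| Version | Men needed for p<0.05 |
|---|---|
| Two-sided exact, zeros dropped | 6 (p=0.031) |
| Two-sided exact, Pratt zeros | 6 (p=0.031) |
| One-sided exact, zeros dropped | 5 (p=0.031) |
| Normal approximation, zeros dropped, no continuity correction | 5 (p=0.043) |
| Same, with continuity correction | 6 (p=0.036) |
| Normal approximation, Pratt zeros | 4 (p=0.046 for n=20 or 40) |
| Normal approximation, zeros split | 6 of 20 (p=0.041); 8 of 40 (p=0.036) |

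With zeros split, 6 of 40 gives p=0.101, so that version does depend on n. Every threshold for n=20 or 40 is still well below half the men.

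5. Chance of at least 6 detections, binomial:

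| Assumed detection rate | n=16 | n=20 | n=32 | n=40 |
|---|---|---|---|---|
| 10% | 0.003 | 0.011 | 0.094 | 0.206 |
| 20% | 0.082 | 0.196 | 0.640 | 0.839 |
| 30% | 0.340 | 0.584 | 0.949 | 0.991 |

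At all these rates the true median is below quantification. For n=20 at 30%, P(K≥10) = 0.048, so the chance that the result is significant and the observed median is also below the limit is 0.584 − 0.048 = 0.536.

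**Reading B: only measured pairs.** A Phase II or III man has a measured pre-drug level only if he also took part in Phase I, which the Abstract allows but does not require. If men keep their arm, that is at most 5 pairs per arm and 10 pooled.

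6. Five of five positive gives 2 × (1/2)^5 = 0.0625, so the two-sided exact test cannot reach p<0.05 within an arm. One-sided exact (0.031) or the uncorrected normal approximation (0.043) could, but only with all five pairs present and all positive.
7. Ten of ten pooled gives 2 × (1/2)^10 = 0.002, but pooling mixes the two products.

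**The case against.** A reader might infer that the SAP contains a fixed six-man rule that holds whatever the sample size. It does not. The SAP names no version of the test, standard versions need 4 to 8 men, and one of them depends on n.

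A reader might also infer that the problem arises in the design as scheduled, with 20 or 40 measured pairs. The documents do not support that. Those pairs exist only if an unmeasured baseline is filled in. With measured pairs in the usual version, 6 detections among at most 10 pooled men is at least 60%, so the follow-up median would be above quantification. If the first on-drug sample were called baseline, differences could be negative and the arithmetic of Reading A would not apply; but the test would then no longer compare with a pre-drug level.

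Nor do the documents show that any compartment will have low detection. The rates above are illustrations.

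Two further points stand in part. Six rises and no falls is valid evidence that levels rose in some men, so the fault is in the label of a difference in medians and not a false positive in the ordinary sense. The SAP also requires the medians to be reported, so an attentive reader would see two below-limit medians beside the p-value. That limits the harm, but it leaves the stated criterion contradicting the summary printed next to it.

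Finally, the Abstract rests the penetration question on the comparison between arms. The SAP has no such test, and this point does not supply one.

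**Conclusion.** The concern holds in a conditional form. With baseline taken as below quantification for all men, the stated test is a test against a structural zero. In the usual two-sided exact version 6 men suffice, and both medians can then be below the limit. With measured pairs only, the same version cannot reach significance within an arm. Under either reading the test does not show whether the drug typically reaches a compartment.

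Reading A rests on the assumption about pre-drug levels and matters only where fewer than half the men have measurable drug. Reading B assumes that men who join a second phase keep their arm. The 58% figure rests on an assumed 30% detection rate with n=20. Where nearly all men have measurable drug, the test gives no misleading answer, but it adds nothing to the description.

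**What to change.** Replace the baseline signed-rank test in the SAP.

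- For each arm, phase, time point and compartment, report the proportion of men with quantifiable drug (exact 95% CI) and the median with its 95% CI, ranking below-limit values lowest.
- State the quantification limit for each assay and matrix.
- Make no claim of a difference in medians when the follow-up median is below quantification. No numerical bar for penetration is proposed, because the documents define none.
- Keep paired signed-rank tests only for compartments sampled at two on-drug visits in the same phase: blood, urine, penile and urethral swabs (4 to 6 h against 24 h in Phase II; 3 to 5 days against 10 days in Phase III). State sidedness, zero handling and the rule for below-limit values.
- Rectal tissue and secretions have one on-drug sample per phase and get the descriptive estimates only.

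The cost is SAP wording and a few lines of code, with no new data. The downside is that fewer compartments will be called positive.
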